3.6 Sample Size

Based on a power of 80% ($\beta=0.2$), alpha of 0.05, a response anticipated difference of 90% in ultrasound-guided fistuloplasty group and 52.4% in fluoroscopy-guided fistuloplasty group, the calculated sample size for each group is 22 patients. Allowing for 20% dropout, a final sample size of 27 per group will be used.

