Study Population	All adult patients with arteriovenous access flow dysfunction in Hospital Kuala Lumpur and University Malaya Medical Centre during the period 1 July 2023 – 30 June 2024.
Study Design	A randomized controlled study. Selected subjects will be randomized into ultrasound-guided fistuloplasty and fluoroscopy-guided fistuloplasty groups in a ratio of 1:1
General Objective	To investigate patencies in patients with arteriovenous access flow dysfunction receiving ultrasound-guided fistuloplasty versus fluoroscopy-guided fistuloplasty at 6 months
Specific Objectives	
 To investigate patencies in patients with arteriovenous access flow dysfunction receiving ultrasound-guided fistuloplasty versus fluoroscopy-guided fistuloplasty at 6 months, To capture data regarding variables that may affect patency of arteriovenous access flow dysfunction post ultrasound-guided fistuloplasty versus fluoroscopy-guided fistuloplasty, To compare technical success in patients with arteriovenous access flow dysfunction receiving ultrasound-guided fistuloplasty versus fluoroscopy-guided fistuloplasty, and To compare complication rates in patients with arteriovenous access flow dysfunction receiving ultrasound-guided fistuloplasty versus fluoroscopy-guided fistuloplasty.
Study endpoints/outcomes	(a) Patency of arteriovenous fistula over a period of six months post fistuloplasty; (b) Resolution of symptoms; (c) Technical success; (d) Percentage increase in volume flow.
Sample Size	54 subjects.
Study Duration	1 July 2023 - 31 December 2024.

1. Background and Significance

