3.1 Study Type and Design

This is an experimental study employing a prospective randomized controlled trial.

The primary outcome would be to compare the patency of arteriovenous fistula at one, three and six months.

Secondary outcomes shall include:

- To capture data regarding variables that may affect patency of arteriovenous access flow dysfunction post ultrasound-guided fistuloplasty versus fluoroscopy-guided fistuloplasty,
- To compare technical success (defined as clinical palpable thrill, radiographic finding of less than 30% recoil and ultrasonographic finding of continuous segment of dilated vein to 5-6mm and continuous flow rate of more than 500ml/min) in patients with arteriovenous access flow dysfunction receiving ultrasound-guided fistuloplasty versus fluoroscopy-guided fistuloplasty and
- To compare complication rates in patients with arteriovenous access flow dysfunction receiving ultrasound-guided fistuloplasty versus fluoroscopy-guided fistuloplasty

Patients are randomized using simple randomization method. Treatment plans are divided equally between ultrasound-guided fistuloplasty and fluoroscopy-guided fistuloplasty. An application “sealedenvelope.com” is used for this purpose. The application does this via a built in random number generator.

After assessing for eligibility, patients will be randomized equally with a ratio 1:1 to ultrasound-guided fistuloplasty group and fluoroscopy-guided fistuloplasty group.

Both interventions will be done in operation theatre to maintain sterility. After cleaning and draping the area of interest, local anaesthesia is given to the puncture site. A puncture needle is used to gain access to the arteriovenous fistula followed by a guide wire. Then, a sheath with an appropriate size is placed and a balloon catheter of adequate size is inserted over the guide wire and inflated for 2 minutes. Ultrasound is used in the subject group to monitor technical success. On table visualization of continuous segment of dilated vein to 5-6mm and continuous flow rate of more than 500ml/min signifies the end points of the procedure.

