3.8 Study Visits and Procedures

Follow-up will be done at two weeks, one month, three months and six months.

Assessment during follow-up includes:

- Resolution of symptoms (prolonged post dialysis bleeding or difficult access cannulation).
- Reduction of venous dialysis pressure to below predefined threshold values. (the acceptable value is less than 150mmHg)
- Measurement of the volume flow (the acceptable value is more than 500ml/min), flow characteristics (the acceptable characteristic is laminar flow) and diameter of the target lesion (the acceptable diameter is between 5-6mm) using duplex ultrasound.

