3.9 Statistical Analysis Plan

The data analysis will be done using the SPSS version 26.0 Descriptive date will be expressed as mean \pm standard deviation (SD) for numerical data and frequency (percentage) for categorical data. Independent t-test will be used to analyse the primary objective. Secondary objective will be analyzed using logistic regression. A value of $P < 0.05$ is considered statistically significant. The data collected will be analyzed using an per protocol basis.

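### The primary patency analysis is per protocol, with about 10 of 54 patients expected to be lost and no rule for using their data, so the result depends on who leaves and the plan has no check on this

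*Combined protocol and SAP*

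**What the plan says.** Section 3.6 finds that "the calculated sample size for each group is 22 patients", assuming "a response anticipated difference of 90% in ultrasound-guided fistuloplasty group and 52.4% in fluoroscopy-guided fistuloplasty group", and continues: "Allowing for 20% dropout, a final sample size of 27 per group will be used".

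Section 3.9 says: "Independent t-test will be used to analyse the primary objective". It puts the whole analysis on a per protocol basis without defining that set. It names no intention-to-treat set, censoring rule, missing-data rule or sensitivity analysis.

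The synopsis words endpoint (a) as "Patency of arteriovenous fistula over a period of six months post fistuloplasty". Section 3.1 puts the primary comparison at months 1, 3 and 6. Section 3.8 sets the visits: "Follow-up will be done at two weeks, one month, three months and six months".

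Two other provisions bear on this. Section 3.5 asks withdrawn patients to come to the final visit and does not replace them. Section 3.1 provides that an ultrasound patient with a poor first follow-up caused by a stenosis that ultrasound missed crosses over to fluoroscopy. No cross-over in the other direction is described.

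**The concern.** The trial is sized on the patients who remain, and a per protocol analysis is then specified. Nothing says how a patient who withdraws, dies, is lost or crosses over enters the primary comparison. The natural reading is that such patients are left out.

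Leaving them out is harmless only if leaving is unrelated to patency, and here that is doubtful. A failing access may itself be why a patient stops attending or is withdrawn by the investigator. The cross-over takes patients from the ultrasound arm only, because their first result was poor. A per protocol set that excluded them would remove ultrasound failures with no matching removal from the fluoroscopy arm.

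At stake is a conclusion that could depend on about a fifth of the patients, with no planned analysis to show how far. If the treatment of those patients is chosen after the data are seen, that choice could settle the result.

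**Working it through.** **1. Inputs.** From section 3.6: patency 90% and 52.4%, alpha 0.05 (two-sided assumed, since sidedness is not stated), power 80%, 22 per arm raised to 27, dropout 20%. From section 3.1: 1:1 allocation. From section 3.9: t-test, per protocol.

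**2. The plan's sample size.** Two-proportion formula, pooled variance under the null, no continuity correction, mean rate (0.90 + 0.524)/2 = 0.712:

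n = [1.960 × √(2 × 0.712 × 0.288) + 0.842 × √(0.90 × 0.10 + 0.524 × 0.476)]² / 0.376² = (1.255 + 0.490)² / 0.1414 = 21.55, rounded up to 22.

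Then 21.55/0.8 = 26.9, rounded up to 27. The plan's figures reproduce. (Starting from the rounded 22, 22/0.8 = 27.5 would give 28; nothing here turns on that.)

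**3. Expected loss.** 54 − 44 = 10 patients by the plan's own figures, or 0.20 × 54 = 10.8. This is 18.5% to 20% of those randomised, about five per arm.

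**4. How far the missing patients can move the result.** The illustration takes 22 completers per arm with counts near the planned rates: 20/22 (90.9%) and 12/22 (54.5%). Patency is scored 0/1, five patients are missing in each arm, and the t-test uses equal variances.

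| Case | Ultrasound | Fluoroscopy | Difference | t-test P | Fisher P |
|---|---|---|---|---|---|
| Completers only | 20/22 | 12/22 | 36 points | 0.006 | 0.016 |
| All missing failed | 20/27 | 12/27 | 30 points | 0.027 | 0.051 |
| All missing patent | 25/27 | 17/27 | 30 points | 0.008 | 0.019 |
| Least favourable to ultrasound | 20/27 | 17/27 | 11 points | 0.39 | 0.56 |
| Most favourable to ultrasound | 25/27 | 12/27 | 48 points | <0.001 | <0.001 |

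The difference runs from 11 to 48 points. Under the plan's t-test, significance is lost only in the least favourable case, and even there ultrasound leads by 74% to 63%. Missing = failed crosses 0.05 only under Fisher's test, which the plan does not name.

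**5. Information left unused.** This was simulated with 27 per arm, constant hazards giving 90% and 52.4% patency at six months, 20% dropout per arm unrelated to patency, and the four scheduled visits. A log-rank test on all randomised patients has about 84% power, against about 81% for a comparison of completers' proportions. Varying the shape of the hazard and using the completers' t-test leaves the gain at about 2 to 4 points. Under constant hazards the dropouts carry about 19 patient-months of follow-up and about one observed loss of patency.

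**The case against.** A dropout allowance is routine and is not an error in itself. That only completers are compared is an inference: section 3.9 does not define its per protocol set, and the set could be drawn more widely. This stands as a limit on the wording, but nothing in the plan points to a wider set.

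A reader might infer that a patient last seen patent at month 3 contributes nothing. The documents do not support that. Section 3.1 names comparisons at months 1, 3 and 6, so such a patient could count in two of the three. Nor are all ten patients' data necessarily lost: section 3.5 asks withdrawn patients to attend the final visit, and anyone leaving before two weeks has no patency time to lose. What remains is that no section says how any of these data are used.

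A reader might also infer that the missing patients could reverse the conclusion. In the illustration they cannot: direction holds in every case, and significance under the t-test goes only at the extreme.

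The efficiency argument is weak, since the power gain is small. Censoring is also not a cure. Kaplan-Meier and log-rank methods assume that leaving is unrelated to patency, so a patient who stays away because the fistula failed would be censored as patent. This stands, and it is why sensitivity analyses are needed. Finally, the eligibility criteria already screen out short life expectancy and planned transplant or abandonment, which makes those exits less likely; unplanned ones remain.

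**Conclusion.** The concern holds in a limited form. The plan commits the primary analysis to an undefined per protocol set, expects about 10 of 54 patients to be lost, and has no rule for their data or for ultrasound patients who cross over. The comparison is biased if leaving is related to patency, and the plan has no analysis that would show it.

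In the illustration, five missing patients per arm can move the difference to anywhere from 11 to 48 points. Missing = failed keeps significance under the t-test; the least favourable case loses it without changing direction. These figures assume completers near the planned rates, patency scored as 0/1, and exactly five missing per arm. The small power gain assumes dropout unrelated to patency and is not the reason to act. The reason is bias, and the need to fix the handling of these patients before results are known.

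**What to change.** In section 3.9:

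- **Population.** Make the primary analysis all randomised patients in their allocated arm, including those who cross over and any final-visit data from withdrawn patients. Define the per protocol set and keep it as supportive.
- **Method.** Analyse time to the first visit with loss of patency. Report Kaplan-Meier patency at six months by arm, the difference with its 95% CI, and a log-rank test grouped by visit.
- **Leavers.** Censor patients who die, are transplanted or move away with a patent access at the last visit known patent. Count access abandoned because of access failure as loss of patency.
- **Sensitivity analyses.** Because censoring still assumes uninformative dropout, add missing = failed and the case least favourable to the better arm.
- **Definition.** State one definition of loss of patency, built from the measures already taken at the visits, including how a repeat procedure after cross-over counts. Section 3.8 lists acceptable values but does not combine them into one outcome.

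The cost is SAP wording. SPSS, the package named in section 3.9, runs Kaplan-Meier and log-rank analyses, and no visits or measurements are added.

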3.7 Study Duration and Timeline

- Stage 1, data collection and data analysis - 8-12 months.
- Stage 2, follow-up - 6 months.
- Stage 3, presentation and publication - 6-12 months.

The participation duration for each subject is 6 months.

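### Section 3.7 lists data analysis before the six-month follow-up stage and none after it, and no other section says when the primary comparison is made

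*Combined protocol and SAP*

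**What the plan says.** Section 3.7 sets out three numbered stages:

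- "Stage 1, data collection and data analysis - 8-12 months"
- "Stage 2, follow-up - 6 months"
- "Stage 3, presentation and publication - 6-12 months"

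It adds: "The participation duration for each subject is 6 months". Analysis appears once, in Stage 1.

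The synopsis sets the general objective at 6 months, and its first endpoint is "Patency of arteriovenous fistula over a period of six months post fistuloplasty". Section 3.1 is broader: "The primary outcome would be to compare the patency of arteriovenous fistula at one, three and six months".

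The synopsis and section 3.2 give a recruitment window of 1 July 2023 to 30 June 2024. The synopsis gives the study duration as "1 July 2023 - 31 December 2024".

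Section 3.9 names the software, an independent t-test for the primary objective, logistic regression for the secondary objective and a 0.05 significance level. It gives no analysis time, data cut-off or data lock, and it mentions no interim analysis.

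**The concern.** A comparison of six-month patency needs the six-month readings, yet the one place that dates the analysis puts it ahead of the follow-up stage. No other section corrects this. The synopsis dates allow 12 months of recruitment and 6 more months, so the study ends at about the time the last patient's six-month visit falls due, which leaves no period for analysis after that visit.

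Anyone who followed section 3.7 literally would test the arms on incomplete six-month data and lose much of the power that the 54 patients were meant to provide. If the test were then repeated on the full data, it would be a second, unplanned look at the same 0.05 level. The protocol describes no blinded outcome assessment, so a result by arm that became known during follow-up could also colour later readings. Nothing in the documents says that such a result would be circulated.

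**Working it through.** **Inputs.** Rates of 90% and 52.4%, alpha 0.05 (taken as two-sided; the plan does not say), power 80%, 22 per group and 27 after 20% dropout (section 3.6). Recruitment window of 12 months (synopsis and section 3.2). Stage lengths (section 3.7).

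**1. The plan's sample size.** Two proportions, pooled variance under the null, no continuity correction. The difference is 0.376 and the mean rate is 0.712.

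n = [1.960 × √(2 × 0.712 × 0.288) + 0.842 × √(0.9 × 0.1 + 0.524 × 0.476)]² / 0.376² = [1.960 × 0.6404 + 0.842 × 0.5826]² / 0.1414 = 21.6, so 22 per group. This matches the plan. The stated 27 corresponds to 22 × 1.2 = 26.4, rounded up.

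**2. Share of readings available at the end of Stage 1.** Assume that Stage 1 is the recruitment period, T months long, and that patients enter evenly. The share with a reading due at month m is (T − m)/T. With T = 12:

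| Reading | Share available |
|---|---|
| 1 month | 11/12 = 92% |
| 3 months | 9/12 = 75% |
| 6 months | 6/12 = 50% |

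If accrual is uneven, with a cumulative share of (t/T)^k, the six-month figure runs from 71% (front-loaded, k = 0.5) to 25% (back-loaded, k = 2). An 8-month Stage 1, the lower limit in section 3.7, would give 2/8 = 25% under even entry, but it does not match the 12-month window.

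**3. Power on half of the six-month readings.** Half of 22 is 11 per arm.

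- Normal approximation, the formula of step 1 solved for power: (0.376 × √11 − 1.960 × 0.6404)/0.5826 = −0.014, so power is 49.4%.
- Exact enumeration of the t-test on 0/1 patency status: 48.9% with 11 per arm, against 82.6% with 22.
- With no dropout by then, 27 × 0.5 = 13.5 per arm, and the approximation gives 59%.

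**4. Type I error, only if the test were done twice.** Two looks, each at ±1.96, the first on half of the data, have test statistics correlated at √0.5. The chance that at least one is significant under the null is 8.3% by normal approximation.

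**5. Stage lengths against the synopsis.** Shortest total: 8 + 6 + 6 = 20 months. Longest: 12 + 6 + 12 = 30 months. The synopsis period is 18 months. Stages 1 and 2 at their longest give 12 + 6 = 18, so the synopsis may leave out Stage 3, but no section says so.

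**The case against.** The strongest reply is that the stage list is a loosely worded timeline and not an analysis plan. Section 3.9 describes one analysis and no interim look, six-month visits are scheduled in sections 3.1 and 3.8, and a six-month comparison cannot be made without them. Data collection is also confined to Stage 1. Read just as strictly, that would mean no data are collected during follow-up, which section 3.8 contradicts. This stands as a reason to doubt that an early comparison is intended. It does not supply the missing analysis time.

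A reader might infer three stronger things, and the documents support none of them.

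- *That the arms will be compared when only 25–50% of the primary outcomes exist.* No section plans that comparison. The range needs even accrual and Stage 1 equal to recruitment, and its lower end needs an 8-month Stage 1. It also covers only the six-month reading, whereas section 3.1 makes one- and three-month patency primary too, and most of those readings would exist.
- *That the type I error is inflated.* This needs a second look that is not planned. It is also an alternative to the power loss and not an addition to it: 49% power assumes that the Stage 1 test is the only one. The 8.3% is not fixed either. Exact enumeration with looks at 11 and 22 per arm gives 8.4%, 7.6% and 5.0% at common patency rates of 52.4%, 71.2% and 90%.
- *That the synopsis dates confirm an early analysis.* They fit recruitment followed by six months of follow-up, and say nothing about when the analysis is done.

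**Conclusion.** The point holds as a conflict in stated timing. Section 3.7 puts the analysis before the follow-up that the six-month objective needs, and nothing else in the protocol or SAP sets the time. Whether an early comparison is intended cannot be told from the documents.

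If the list were followed, the six-month comparison would rest on about half of its readings, with power near 49% against a planned 80%. That size depends on the 12-month window, even accrual, Stage 1 equal to recruitment, and the plan's own rates and dropout. Uneven accrual moves the share between 25% and 71%. A type I error of roughly 8% would arise only if the test were repeated at the end. The change is worth making because it costs little and the trial is small.

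**What to change.** 1. In section 3.7, reword Stage 1 as recruitment, procedures and data entry, with no comparison by arm.
2. Place the analysis after the last six-month visit and data lock, at the start of Stage 3.
3. Add to section 3.9, for example: *There is no interim analysis. Outcomes will not be tabulated or tested by arm until all six-month visits are complete and the data are locked.*
4. Reconcile the 20 to 30 months of stages in section 3.7 with the 18 months in the synopsis, and say whether the synopsis period includes analysis and reporting.

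The cost is wording in sections 3.7 and 3.9 and possibly the synopsis. Sample size, visits and tests are unchanged. The one downside is that no results by arm can be presented early.

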3.8 Study Visits and Procedures

Follow-up will be done at two weeks, one month, three months and six months.

Assessment during follow-up includes:

- Resolution of symptoms (prolonged post dialysis bleeding or difficult access cannulation).
- Reduction of venous dialysis pressure to below predefined threshold values. (the acceptable value is less than 150mmHg)
- Measurement of the volume flow (the acceptable value is more than 500ml/min), flow characteristics (the acceptable characteristic is laminar flow) and diameter of the target lesion (the acceptable diameter is between 5-6mm) using duplex ultrasound.

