Fluoroscopy is used in the control group to assess for technical success. On table fistulogram visualization of less than 30% recoil of the target lesion signifies technical success. After a satisfactory result, a figure of 8 suture is placed with manual inflow occlusion. Post procedure, patients will be observed for any signs of haematoma or bleeding. If there are no immediate complications, patients will be discharged on the same day.

These procedures will be performed either by vascular surgeons or interventional radiologists below tabled:

OPERATOR	FISTULOPLASTY		CENTRE	DESIGNATION
	ULTRASOUND-GUIDED	FLUOROSCOPY-GUIDED		
[name] [name]	✓		University Malaya Medical Centre	Vascular surgeon
TBD		✓	University Malaya Medical Centre	Interventional radiologist
[name] [name]	✓	✓	Hospital Kuala Lumpur	Vascular surgeon

Cases with serious complications such as extravascular leak or significant pseudoaneurysm will be admitted for monitoring. If the complications are resolved then, the patient will be discharged. Follow-up may be scheduled earlier.

Follow-up will be done at two weeks, one month, three months and six months.

Assessment during follow-up includes:

- Resolution of symptoms (prolonged post dialysis bleeding or difficult access cannulation).
- Reduction of venous dialysis pressure to below predefined threshold values. (the acceptable value is less than 150mmHg)
- Measurement of the volume flow (the acceptable value is more than 500ml/min), flow characteristics (the acceptable characteristic is laminar flow) and diameter of the target lesion (the acceptable diameter is between 5-6mm) using duplex ultrasound.

[figure not shown]
In the event of a negative outcome during the first post fistuloplasty follow-up, it will be determined whether it is due to:

- a missed stenotic segment invisible to ultrasound or
- it is a case of severe stenotic segment refractory to fistuloplasty.

Patients belonging to the former category will cross-over to the fluoroscopic-guided fistuloplasty group. In the latter case, there is no reason to repeat the fistuloplasty regardless of the imaging method (ultrasound or fluoroscopy). Ideally, these particular patients should receive drug-coated balloon (DCB) fistuloplasty which is beyond the scope of this study. There is no alternative apart from switching to fluoroscopic-guided fistuloplasty.

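### No rule scores symptom resolution or flow change once a fistula is lost or re-treated, and the per-protocol basis leaves those failures open to removal or mis-scoring

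*Combined protocol and SAP*

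**What the plan says.** The synopsis names, after patency, the endpoints "b) Resolution of symptoms; (c) Technical success; (d) Percentage increase in volume flow". Sections 3.1 and 3.8 give the same follow-up assessments at two weeks and one, three and six months. Symptoms are assessed as "Resolution of symptoms (prolonged post dialysis bleeding or difficult access cannulation", and flow by duplex ultrasound: "Measurement of the volume flow (the acceptable value is more than 500ml/min), flow characteristics".

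Section 3.1 describes what happens after a negative result at the first follow-up. For a stenosis that ultrasound missed, "Patients belonging to the former category will cross-over to the fluoroscopic-guided fistuloplasty group". For a refractory stenosis it says both that repeating the procedure has no rationale under either imaging method and that a switch to fluoroscopy is the only alternative. Those two statements need to be reconciled, because they determine how many patients are re-treated.

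Section 3.9 names one analysis basis: "The data collected will be analyzed using an per protocol basis". It does not define that set and gives no missing-data rule. Section 3.4 excludes planned abandonment of the access at entry. Section 3.5 asks withdrawn subjects to attend the final visit. Neither says how a fistula lost during follow-up is scored on (b) or (d).

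**The concern.** Bleeding after dialysis and difficult needling can be seen only in a fistula that is in use. A thrombosed or abandoned fistula shows neither sign. Unless a rule says otherwise, the patient with the worst outcome is either unscorable on (b) or, on a literal reading, free of symptoms.

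Re-treatment raises a second problem, which affects both endpoints. Once a patient has had another procedure, later symptoms and flow reflect that procedure and not the one assigned. Section 3.1 writes this route for the ultrasound arm. Keeping the later values credits ultrasound with the result of fluoroscopy. Removing the patient as a protocol departure takes treatment failures out of one arm.

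At stake is whether the comparisons on (b) and (d) remain randomised comparisons. The patients in doubt are the failures. If the arms fail at different rates, any unwritten choice about them acts unequally, and it could be made after the results are seen.

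**Working it through.** **Inputs from the documents.** Section 3.6 gives "a response anticipated difference of 90% in ultrasound-guided fistuloplasty group and 52.4% in fluoroscopy-guided fistuloplasty group", 80% power, alpha 0.05, 22 per group and 27 after the dropout allowance. With p̄ = (0.90 + 0.524)/2 = 0.712, the usual two-sided formula with pooled variance and no continuity correction gives

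n = [1.96·√(2·0.712·0.288) + 0.842·√(0.90·0.10 + 0.524·0.476)]² / 0.376² ≈ 21.6, so 22 per group.

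This matches the plan. Then 22 × 1.2 = 26.4, so 27, which also matches.

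**Expected failures, if response means six-month patency.** Ultrasound: 27 × 0.10 = 2.7. Fluoroscopy: 27 × 0.476 = 12.9. Together 15.6 of 54, or 29%.

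**Assumptions that the documents do not supply.**
- r = 0.80 of patent fistulas have symptoms resolved.
- f is the share of non-patent fistulas that can no longer be used. The documents give no figure, so a range is shown.
- A non-patent fistula still in use counts as unresolved.

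**Endpoint (b).** With patency p, the proportion resolved is:
- lost fistula counted as failure: p·r
- lost fistula left out: p·r / [1 − (1 − p)·f]
- lost fistula read literally as symptom-free: p·r + (1 − p)·f

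Counted as failure, the rates are 0.90 × 0.80 = 72.0% and 0.524 × 0.80 = 41.9%, a difference of 30.1 points whatever f is.

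| f | Left out: US, fluoroscopy | Difference | Literal: US, fluoroscopy | Difference |
|---|---|---|---|---|
| 5% | 72.4%, 42.9% | 29.4 | 72.5%, 44.3% | 28.2 |
| 25% | 73.8%, 47.6% | 26.3 | 74.5%, 53.8% | 20.7 |
| 50% | 75.8%, 55.0% | 20.8 | 77.0%, 65.7% | 11.3 |
| 100% | 80.0%, 80.0% | 0.0 | 82.0%, 89.5% | −7.5 |

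The literal difference equals (0.90 − 0.524)·(r − f), so its sign changes only when f exceeds r, here 80%. Leaving patients out removes the difference completely only at f = 100%. With r = 0.70 or 0.90, the failure-scored difference is 26.3 or 33.8 points.

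**Endpoint (d).** Assume a gain of 100% in patent fistulas, 0% in usable failures and −100% for zero flow. The mean difference is then:

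| f | Lost fistulas left out | Lost fistulas entered as −100% |
|---|---|---|
| 5% | 36.8 | 39.5 |
| 25% | 32.8 | 47.0 |
| 50% | 26.0 | 56.4 |
| 100% | 0.0 | 75.2 |

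At 5%, for example: 90/0.995 − 52.4/0.9762 = 36.8, and 89.5 − 50.0 = 39.5 (percentage points). In this model (d) is attenuated and never reversed.

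These tables cover lost fistulas only. The documents give no rate for re-treatment, so its effect is not quantified.

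**The case against.** Several stronger readings are tempting, and the documents do not support them.

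- **That the plan drops lost fistulas or scores them as resolved.** It prescribes neither. Thrombosis is an outcome and not a protocol deviation, Section 3.5 does not list access loss as a reason for withdrawal, and the per-protocol set is undefined. Removal is likely for cross-overs and only possible for lost fistulas.
- **That (d) also needs a fistula in dialysis use.** Flow is a duplex reading, and an occluded fistula can be entered as zero. Nothing can be recorded as resolved on (d).
- **That the arm difference will be hidden or reversed.** This needs nearly all failures to be unusable, and reversal also needs literal scoring. The thrombosis figures in Section 3.11 are 1%, 1.9% and 2.2%. They are complication rates and not six-month abandonment, but they make a low share worth showing. At 5% the distortion of (b) is under 2 points.
- **That the plan certainly expects unequal loss.** Section 3.6 does not define response. Section 3.11 argues that, with adequate images, outcomes should be much the same under either method. Appendix 1 lists 90% six-month patency for fluoroscopy. If patency, the unusable share and the resolution rate are equal in both arms, scoring of lost fistulas creates no bias between them.
- **That refractory cases leave the study.** Section 3.1 does not say so. It places drug-coated balloon treatment outside the study's scope but then names a switch to fluoroscopy as the only alternative.

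It is also fair that neither endpoint appears in the outcome list of Section 3.1, that the sample size does not rest on them, and that access loss should still show in the primary patency outcome. These points limit the consequence. They do not supply the missing rule, and they do not make per protocol a suitable basis for endpoints on which failures are the patients in doubt.

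**Conclusion.** The concern holds for (b) and (d) and should be acted on. It does not reach the primary comparison. Endpoint (b) cannot be observed in a fistula that is no longer needled, both endpoints change meaning after re-treatment, no rule covers either case, and the stated analysis basis makes exclusion of cross-overs likely.

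For (b), over unusable shares of 5% to 50% of failures, the loss from a true 30.1 points is 0.7 to 9.3 points if such patients are left out and 1.9 to 18.8 points if they are read as symptom-free. These sizes rest on reading the Section 3.6 response as six-month patency, on an assumed 80% resolution rate, and on an assumed range for the unusable share. For (d), the risk is missing values or values that belong to a second procedure. The direction of bias depends on which arm loses more fistulas: leaving failures out, or reading them as symptom-free, favours that arm.

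**What to change.** Add to Sections 3.8 and 3.9, as analysis rules only, with no change to clinical management:

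1. Analyse (b) and (d) in all randomised patients, in the arm assigned.
2. For (b), count thrombosis, abandonment for access failure, or any repeat or surgical access procedure as not resolved from that date.
3. For (d), enter 0 ml/min (−100%) for a thrombosed or abandoned fistula. Give a re-treated fistula the lowest rank, tied with zero flow. Compare arms by a rank test.
4. Report the number of fistulas lost and re-treated in each arm, with deaths and transplants shown separately so that they are not counted as access failure.
5. Give symptom and flow results among still-patent fistulas as descriptive only.

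The cost is a few sentences. No new visits or measurements are needed, since access in use and repeat procedures should be known from dialysis records and the planned follow-up. The sample size is unaffected. The downside is that rates look less favourable in both arms, (b) moves closer to a patency composite, and (d) is reported as a rank comparison instead of a simple mean.
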